This study is designed to investigate the efficiency of biofilm decontamination of Er:YAG laser compared to carbon fiber curette. The first phase is clinical wherein experimental subjects will be recruited. Full periodontal examination will be performed and alginate impressions will be taken. A custom mouth guard that holds multiple titanium discs will be fabricated. Experimental subjects will be instructed to wear this mouth guard for 72 hours, during which time a natural bacterial biofilm will form on the disc surfaces. The second phase of the study will be performed after collecting the discs from the subjects and exposing them *ex vivo* to one of four treatment groups 1) Er:YAG laser, 2) carbon fiber curette, 3) titanium brush, and 4) no treatment (control). The biofilm will be stained with LIVE/DEAD *BacLight* dye and the residual biofilm will be visualized under fluorescence microscopy. Quantification of residual biofilm will be performed using image analysis software (Image J, NIH). Statistical methods will be used to determine the significance of each treatment modality. The primary outcome of the study is the percent area of the titanium disc covered by biofilm.

B) Power Calculation

A power calculation was performed via the statistical software nQuery Advisor (Version 7.0). Using the results of Schwarz et al.⁴² for anticipated means and standard deviations, and assuming that the mean for the combination group is equal to the mean of the Er:YAG laser group, a sample of 8 subjects, allowing for ~20% dropout with a final projected sample size of 6 (8 discs per subject, 64 total discs) is sufficient for a Type I error rate of 5% and a power over 99%. Discs retrieved from each mouth guard will be randomized over the 4 treatment groups using the "sample" function of the statistical software package R (Version 3.1.2), so that each subject will contribute two discs to each treatment group.

C) Statistical analysis

Descriptive statistics (means, standard deviations, medians, and inter-quartile ranges) will be computed by group. Statistical significance will be assessed via repeated-measures ANOVA if the data are normally distributed, and Friedman's test if the data are not normally distributed. $P < 0.05$ will be considered statistically significant. The analysis will be conducted using SPSS Version 22.

D) Products

Titanium discs will be supplied by Straumann USA (Andover, MA).

E) Subject Characteristics

Inclusion criteria:

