measuring pocket depth, recession, attachment level, and bleeding on probing. If full periodontal examination was performed at TUSDM no more than 6 months ago, then existing records may be used to determine eligibility. As periodontal measurements are not a primary outcome, existing periodontal measurements collected by other TUSDM dentists may be used.

Inclusion and exclusion criteria will be considered and eligibility for the study will be determined.

Alginate impression for the maxillary teeth will be taken using stock plastic trays according to subject's arch size in conformance with standard of care practice.

After Visit 1 (In the Laboratory): Impression pouring, cast, and mouth guard fabrication

After the visit, alginate impressions will be disinfected and poured in the dental laboratory using dental stone. Subjects are not required to stay for the length of time of laboratory procedures. Dental stone will be allowed to set for 45 minutes before cast retrieval. After retrieval, casts will be trimmed according to laboratory standards. Titanium discs (5mm diameter, 1 mm thick, 4 discs each on the left and right premolar/molar areas, a total of 8 discs per subject, supplied by Straumann USA) will be fixed on the buccal surfaces of posterior teeth of the casts. A computerized positive pressure thermal-molding machine (Biostar, Great Lakes Orthodontics, Tonawanda, NY) will be used to fabricate a 1mm thick mouth guard on top of the cast, covering the attached titanium discs. The mouth guard will be removed from cast and trimmed to proper size. New titanium discs of the same size and count will be secured in mouth guard compartments with surgical adhesive (PeriAcryl, Salvin Dental Specialties, Charlotte, NC, Figure 1). The final shape of the appliance will resemble an occlusal mouth guard. The mouth guard will be disinfected in 0.12% chlorhexidine.

Figure 1: Gosau et al.⁴³

Visit 2: Within 2 months of Visit 1- Mouth guard delivery (approximately 60 minutes)

Medical history will be reviewed. Eligibility criteria will be re-evaluated. The mouth guard will be inserted into subject's mouth and adjusted for complete fitting and comfort. Intra-oral photograph will be taken in frontal view of the subject's teeth and gums while wearing the mouth guard.

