Subject will be asked to use the mouth guard for 72 hours continuously except during eating. Patient will be instructed to brush their teeth twice daily without the use of toothpaste and to floss once daily. Mouth rinses will be prohibited. These instructions will be given verbally with demonstration facing a mirror. The same instructions will be provided to study subjects in writing as well.

Visit 3: 3 days after Visit 2- Mouth guard retrieval (approximately 30 minutes)

Medical history will be reviewed. Eligibility criteria will be evaluated. Mouth guard will be retrieved from patient and stored until analysis.

After Visit 3(In the laboratory): Group Assigning, Experimental Treatments, and Measurements

After the visit, titanium discs will be separated from the mouth guard. Subjects are not required to stay for the length of time of laboratory procedures. Care will be taken not to disturb the surface biofilm. The back side of each disc will be numbered 1-64 and the subject and intraoral location will be recorded. Discs retrieved from each occlusal mouth guard will be randomized over the 4 treatment groups using the "sample" function of the statistical software package R (Version 3.1.2), so that each subject will contribute two discs to each treatment group.

After treatment, discs will be placed individually in a 24-well tissue culture plate, rinsed with saline and stained using the LIVE/DEAD BacLight dye Kit (Thermo Fisher Scientific, Waltham, MA). Equal volumes of Component A and Component B will be combined in a microfuge tube. The dye mixture will be added to the discs and incubated at room temperature in the dark for 15 minutes. The discs will be observed in a fluorescence microscope equipped with FITC/TRITC filter sets (Zeiss Axiovert 200, Carl Zeiss AG, Oberkochen, Germany). Percent biofilm covered area will be calculated with digital image analysis software (ImageJ, NIH).

Appointment Procedures	Visit 1 Screening/ Baseline	Visit 2 Baseline (Treatment Day 0)	Visit 3 Retrieval (Treatment Day 3)
Consent Form	X		
Demographics	X		
Medical/Dental History	X	X	X
Inclusion/Exclusion Criteria	X	X	X
Oral Examination	X		
Digital Photography		X	
Alginate Impressions	X		
Compensation			X

Mouth guard Delivery		X	
Mouth guard Instructions		X	
Mouth guard Retrieval			X

H) Subject Safety

1) Adverse Event Reporting

Adverse Events

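### Disc location is recorded before treatment but used neither in the allocation nor in the analysis, so any front-to-back biofilm difference that survives treatment adds noise, not bias, to the laser-curette comparison

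*Combined protocol and SAP*

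**What the plan says.** Section G (Study Procedures, After Visit 1) sets out the layout of the guard: "4 discs each on the left and right premolar/molar areas, a total of 8 discs per subject". It does not say how many of the four sites on a side are premolar and how many molar.

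Under After Visit 3, each disc is numbered on its back and "the subject and intraoral location will be recorded". Then "Discs retrieved from each occlusal mouth guard will be randomized over the 4 treatment groups", "so that each subject will contribute two discs to each treatment group". No stratification or blocking by location is mentioned.

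The outcome is measured after treatment (Section A, Experimental Design): "The primary outcome of the study is the percent area of the titanium disc covered by biofilm".

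Apart from descriptive statistics by group, Section C gives the whole analysis in one sentence: "Statistical significance will be assessed via repeated-measures ANOVA if the data are normally distributed, and Friedman's test if the data are not normally distributed". It names no location factor or covariate and does not say how the two discs per subject and treatment are combined. Nothing later in the document uses the recorded location.

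**The concern.** Four sites run from front to back on each side, and each treatment receives two of a guard's eight sites at random. Laser and curette discs will therefore often sit at different positions in the same mouth. If plaque forms unevenly along the row and some of that unevenness remains after treatment, part of the observed laser-curette difference reflects where the discs sat. With 6 projected subjects there are 12 discs per arm, so these chance differences are averaged over few guards. The trial already collects the pre-treatment value that would explain this variance. At stake is the precision of the key comparison.

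**Working it through.** **The plan's own figures.** Section B states power above 99% at a 5% type I error rate, with 8 subjects enrolled and 6 projected. The counts agree: 6/(1 − 0.20) = 7.5, rounded up to 8; 8 × 8 = 64 discs. The power cannot be reproduced, because no means, SDs or within-subject correlation are printed.

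**How often positions differ.** Assume two premolar and two molar sites per side. Enumerating every way to draw 2 laser and 2 curette discs from 8 sites gives unequal premolar/molar counts in 63% of guards (by one disc in 46%, by two in 17%). The mean imbalance is exactly 0, so there is no bias. In simulations of a paired test with no treatment effect (n = 6), type I error was 4.6%, 4.9% and 5.3% for premolar-molar steps of 0, 1 and 2 disc-level SDs.

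**Variance of the laser-curette difference in one subject**, each treatment averaged over two discs:

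- Disc noise, SD σ: σ²(1/2 + 1/2) = σ².
- Position, with S the SD of the position effect over the 8 sites (divisor 7), sites drawn without replacement: S²(1/2 + 1/2) = S².
- Subject-by-treatment interaction, SD τ: 2τ².

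The enumeration confirms the position term. A premolar/molar step g gives S² = 8 × 0.25g²/7 = (2/7)g² = 0.286g². A linear gradient of full range g gives 0.159g².

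**Effect on interval width.** S and τ are not in the documents; the values below are assumptions, with σ = 1. Before any cost of estimating the position slope, the unadjusted interval is wider by the factor √[1 + S²/(1 + 2τ²)]. The last column allows for that cost, from simulation with n = 6 and, where τ > 0, the interaction variance taken as known; the second-last row is inferred from the factor and that cost.

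| S | τ | Factor before cost | Unadjusted against adjusted, after cost |
|---|---|---|---|
| 0.5 | 0 | √1.25 = 1.118 | about 10% wider |
| 0.5 | 0.5 | √(1 + 0.25/1.5) = 1.080 | about 6% wider |
| 0.5 | 1 | √(1 + 0.25/3) = 1.041 | about 2% wider |
| 0.25 | 0 | √1.0625 = 1.031 | at most about 2% wider |
| 0.25 | 1 | √(1 + 0.0625/3) = 1.010 | about equal |
| 0 | any | 1.000 | adjusted is about 1% to 3% wider |

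For scale, S = 0.5 means a full front-to-back range of 0.5/√0.159 = 1.25σ if linear, or a premolar/molar step of 0.5/√0.286 = 0.94σ.

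**Effect on power.** Suppose power is exactly 99% with no gradient and n = 6. A paired contrast then needs a mean difference of about 2.24 SDs of the differences. With τ = 0, a step g multiplies the variance by 1 + (2/7)(g/σ)²:

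| g/σ | Variance factor | Paired power | Four-group ANOVA power |
|---|---|---|---|
| 0.25 | 1.02 | 98.9% | 98.9% |
| 0.5 | 1.07 | 98.6% | 98.5% |
| 1 | 1.29 | 96.7% | 96.3% |

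The last row corresponds to S = √0.286 = 0.53.

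**The case against.** The strongest reply is that nothing is invalid. Randomisation within subject already deals fairly with location, recording a location also serves to trace discs, and leaving out a precision covariate is a modelling choice. That stands, and it limits the point to efficiency.

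The documents also give no evidence of a gradient. All discs are buccal, posterior and in one maxillary guard, and effective cleaning could shrink any gradient in the treated arms. That stands too. The table assumes the same additive position effect in all arms.

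A high planned power leaves little to recover. This holds if the stated figure is right, but it cannot be checked, and the power paragraph assumes a mean for a combination arm that is not among the four treatments.

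A reader might infer more than this: that the comparison is biased, or that the trial loses much of its power. The first fails because the expected imbalance is zero. The second needs a position SD about as large as all other disc noise (intervals about 39% wider without interaction), or a treatment difference of only 1 disc-level SD, where power at S = 0.5 is 57% unadjusted against 66% adjusted. The documents support neither assumption, and a 1-SD difference does not fit a plan that claims over 99%.

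Finally, the change is more than an added covariate. It replaces the planned ANOVA, and Friedman's test cannot take a covariate, so that branch must be dealt with explicitly.

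**Conclusion.** The point holds as a low-priority refinement. Location is measured before treatment and then not used, and a gradient that survives treatment would add variance to the laser-curette difference. With 6 subjects and a position SD of half the disc noise, the cost is an interval about 2% to 10% wider, less as the subject-by-treatment interaction grows. At a quarter of the noise SD it is close to nothing. If power is really above 99%, the loss is about 1 point or less for small gradients and a few points at most for moderate ones.

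These sizes rest on an assumed gradient, on averaging the two discs per subject and treatment (which Section C does not specify), on an additive and roughly linear position effect, and on an interaction variance taken as known. With only about six subjects to estimate that variance, the gain in practice is less certain.

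**What to change.** In Section C, prespecify a disc-level linear mixed model for percent covered area, with fixed effects for treatment and recorded front-to-back position (coded 1 to 4 on each side, one linear term) and random effects for subject and subject-by-treatment. Take the laser-curette difference and its interval from this model. Add that Friedman's test on subject-by-treatment means is kept only as an unadjusted sensitivity analysis if residuals are clearly non-normal. This also settles how the two discs per subject and treatment enter the analysis.

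No new data are needed, and SPSS can fit the model. The cost is a short rewrite of Section C, one extra parameter, and an interval about 1% to 3% wider if position has no effect. The term should be fixed before the results are seen, because adding it afterwards would be a post hoc choice. Restricting the allocation by side alone would not replace it, since that leaves a front-to-back gradient in place.

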An adverse event is any untoward or unfavorable medical occurrence in a human subject, including any abnormal physical exam or laboratory finding, symptom, or disease, temporally associated with a subject's participation in the research. An adverse event in this study may be the loss of the mouth guard or the loss of a titanium disc.

Adverse events will be recorded in source documents and on case report forms. All adverse events and non-serious situations will be recorded, monitored, and reported to the IRB at time of continuing review or at the study's termination if this occurs before the study's next continuing review.

Adverse events will be recorded in source documents and on case report forms. All adverse events and non-serious situations will be recorded, monitored, and reported to the IRB at time of continuing review.

Serious Adverse Events

A serious adverse event is one that results in death, or is life-threatening, or results in hospitalization or prolongation of existing hospitalization, or results in a persistent or significant disability/incapacitation, or results in a congenital anomaly/birth defect, or may jeopardize the subject's health and may require medical or surgical intervention to prevent one of the other outcomes listed above. Based on clinical experience with mouth guards it is unlikely that study subjects will experience any serious adverse event. Should a serious adverse events occur, will be recorded in source documents and on case report forms. Serious Adverse Events that meet the criteria of an unanticipated problem will be reported to the IRB within 5 business days following the Reportable New Information Policy. Serious adverse events that do not meet the criteria for an unanticipated problem will be recorded in source documents and on case report forms, and included in the summary reporting form at the continuing review or at the study's termination if this occurs before the study's next continuing review.

Unanticipated Problems

An unanticipated problem is an incident, experience, or outcome that meets all of the following criteria: 1) The nature, severity, or frequency is unexpected for the subject population or research activities as described in the current IRB approved protocol, supporting documents, and the ICF(s); 2) it is related or possibly related to

participation in the research; 3) it suggests the research may place the subject or others at a greater risk of harm than was previously recognized.

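### Optional: randomising each mouth guard's eight discs separately within left and right would remove a possible source of noise at almost no cost; the plan is valid without it

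*Combined protocol and SAP*

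**What the plan says.** Section G (After Visit 1) describes the guard as having "4 discs each on the left and right premolar/molar areas, a total of 8 discs per subject". Section A lists four treatment groups: Er:YAG laser, carbon fiber curette, titanium brush and untreated control.

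After retrieval, section G (After Visit 3) says "Discs retrieved from each occlusal mouth guard will be randomized over the 4 treatment groups using the" sample function of R, "so that each subject will contribute two discs to each treatment group". Section B repeats the rule. Section G also says that "the subject and intraoral location will be recorded" for each disc.

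On analysis, section C states "Statistical significance will be assessed via repeated-measures ANOVA if the data are normally distributed", with Friedman's test otherwise. It names no term for side or position. Section B plans 8 subjects and 64 discs, with 6 subjects projected after dropout, and calls this "sufficient for a Type I error rate of 5% and a power over 99"%.

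Section H foresees incomplete guards: "An adverse event in this study may be the loss of the mouth guard or the loss of a titanium disc".

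**The concern.** The subject is already a block, which is the most important restriction. Within the subject, however, nothing stops both discs of one treatment from coming from the left and both discs of another from the right. If plaque accumulates differently on the two sides of a mouth, that difference enters the within-subject treatment contrast as extra noise. Location is recorded but, as written, it is used neither in the allocation nor in the analysis.

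Because allocation is random, the noise averages to zero over repetitions and no treatment is favoured. What could be lost is precision, and as few as 6 subjects may remain over which chance imbalances can average out. The layout makes the remedy unusually easy: four positions per side match four treatments.

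**Working it through.** **The plan's own figures.** 6/(1 − 0.20) = 7.5, rounded up to 8 subjects; 8 × 8 = 64 discs. Both agree with section B. The power figure cannot be reproduced, because the means and SDs are taken from a cited study and are not given.

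**How often sides are unbalanced.** Allocations of 8 discs, two per treatment: 8!/(2!)⁴ = 2,520. Allocations with every treatment once on each side: 4! × 4! = 576, so 576/2,520 = 22.9%. Let L be a treatment's number of left-side discs. Full enumeration of L(Er:YAG) − L(curette) gives:

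| Difference | Allocations |
|---|---|
| 0 | 936 |
| +1 or −1 | 576 each |
| +2 or −2 | 216 each |

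The two treatments are unequally split in (2 × 576 + 2 × 216)/2,520 = 1,584/2,520 = 62.9% of guards. The mean difference is 0, so there is no bias. Its variance is (1,152 × 1 + 432 × 4)/2,520 = 8/7.

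**Effect on the contrast.** Assumptions, since the documents give no values: left and right differ by δ, σ is the disc SD within a side, and τ² is the subject-by-treatment variance per treatment. With two discs averaged per treatment, the side contribution is δ × (difference in L)/2, so its variance is (8/7)/4 × δ² = (2/7)δ². The within-subject Er:YAG–curette contrast has variance

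- as written: σ² + 2τ² + (2/7)δ²
- randomised within side: σ² + 2τ²

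| Assumed δ | Increase, τ² = 0 | Increase, τ² = 0.5σ² |
|---|---|---|
| 0 | 0% | 0% |
| 0.5σ | 7.1% | 3.6% |
| σ | 28.6% | 14.3% |

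If the laser leaves no side difference on its own discs, only the curette discs contribute: var(L) = 3/7, so the term is (3/7)/4 × δ² = (3/28)δ². With τ² = 0 that is +2.7% at 0.5σ and +11% at σ.

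**Type I error.** In simulations of a paired t test with 6 subjects and unrestricted allocation, the 5% test rejected 4.8% to 5.2% of the time for δ between 0 and 2σ.

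**Power.** Assumed starting point: exactly 99% with 6 subjects for an F test on subject-by-treatment means, with 3 and (4 − 1)(6 − 1) = 15 df. This needs a noncentrality of 30.96, which is then divided by the variance ratio.

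| Assumed δ | Power, τ² = 0 | Power, τ² = 0.5σ² |
|---|---|---|
| 0.5σ | 98.5% | 98.8% |
| σ | 96.3% | 97.9% |

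A paired t test of Er:YAG against curette on 5 df, also started at 99% with τ² = 0, gives 98.6% and 96.7%. A much larger difference, δ = 2σ, would bring that test to about 85%; nothing in the documents suggests one.

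**One disc lost, treatment left short chosen at random.** With seven discs, the finite-population variance of the left indicator is (7/6)(4/7)(3/7) = 2/7. Unrestricted, the side term is (2/7)(1/2 + 1/2) = 2/7 when neither compared treatment is short and (2/7)(1 + 1/2) = 3/7 when one is. Each case has probability 1/2, so the average is 5/14 = 0.357 (in units of δ²). Randomised within side, the contrast is off by ±δ/2 with total probability 1/2, so the term is (1/2)(1/4) = 0.125. Blocking still removes 1 − 0.125/0.357 = 65% of it.

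**The case against.** The strongest reply is that this is a preference and not a fault. Randomising within subject with two discs per treatment is valid, and the layout is symmetric: buccal posterior sites on both sides of one guard. No passage suggests that left and right differ, and at δ = 0 the loss is nil. Section B says over 99%, so the true starting power may be higher: from 99.5% the worst-case figures are 99.2% at 0.5σ and 97.7% at σ, and from 99.9% they are 99.8% and 99.3%. All of this stands, and it is why the point is optional.

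A second reply is that recorded side can be adjusted for in the analysis without touching the randomisation. That is possible, but section C does not plan it, and it recovers less. In a disc-level model with 6 subjects, the contrast variance stays about 3% above the blocked design if one common side effect is fitted, and about 19% above it if a side effect is fitted for each subject.

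A third reply is that lost discs make the change less than free, and that premolar/molar position within a side stays unbalanced. Both are true. They limit the benefit but do not reverse it.

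**Conclusion.** The point holds as an optional improvement. As written, the allocation leaves Er:YAG and curette unequally split by side in 62.9% of guards. The consequence is lost precision, not bias, and only to the extent that biofilm differs between sides. Under assumed differences of up to one within-side disc SD, the variance of the main contrast rises by between 0% and 29%, and an assumed 99% power falls to no lower than 96.3%. These sizes rest on assumed δ, τ² and starting power, none of which the documents supply. The loss is probably small against the stated power, and the plan may proceed unchanged. The case for acting is that the remedy costs almost nothing and only 6 subjects may remain.

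**What to change.** For any guards still to be randomised, permute the four treatments separately over the four left and the four right discs, so that each treatment has one disc per side. With complete guards, averaging a subject's two discs per treatment cancels a common side difference, so the planned repeated-measures ANOVA on those means can be used as it is, with the same error degrees of freedom.

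Add a short rule for lost discs: randomise three of the four treatments, drawn at random, over the three discs left on that side; if each side loses one, leave out a different treatment on each side. The same principle would need a further sentence for two discs lost from one side. Where guards are incomplete, include recorded side as a block term in a disc-level analysis. Recorded location can also serve as a sensitivity check for position within a side.

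The cost is one line of R and one or two sentences for complete guards, plus the lost-disc rule and its disc-level analysis. The 8 subjects, the 64 discs and the two discs per treatment per subject do not change.

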Studies evaluated efficiency of decontamination using scanning light microscopy, scanning electron microscopy (SEM), counting the colony forming units (CFU), bacterial smears, and photometric XTT–formazan evaluations.³¹ Molecular Probes' LIVE/DEAD® BacLight™ Bacterial Viability Kits provide a novel two-color fluorescence assay of bacterial viability that has proven useful for a diverse array of bacterial genera. LIVE/DEAD BacLight allow researchers to easily, reliably and quantitatively distinguish live and dead bacteria in minutes, even in a mixed population containing a range of bacterial types.

Since no consensus treatment for peri-implantitis has yet emerged, there is an urgent need for quantitative evaluation of the available treatment options. This study is designed to compare the biofilm removal efficiency of the Er:YAG laser with mechanical biofilm removal tools. Our goal is to establish whether Er:YAG laser significantly improves titanium surface decontamination. Our findings may contribute to the development of novel and efficient treatment of peri-implantitis.

Standard of Care in the TUSDM Periodontal Clinic

For patients who are experiencing a failing dental implant, the treatment starts with improving overall oral hygiene and controlling any etiological factors that prevent restoration of optimum oral health. The second step usually involves a surgical

intervention method such as open flap debridement, followed by implant decontamination using Er:YAG, titanium brushes, or plastic curettes. If the bony defect developed by the disease process is contained, bone regenerative therapy may be used.

I) Research Plan

A) Experimental Design

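### The available text does not say that whoever images the discs or measures percent biofilm area is unaware of treatment; coded, randomly ordered reading would be a cheap safeguard

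*Combined protocol and SAP*

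**What the plan says.** A) Experimental Design defines the endpoint: "The primary outcome of the study is the percent area of the titanium disc covered by biofilm". It adds that "Quantification of residual biofilm will be performed using image analysis software (Image J, NIH").

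The laboratory section after Visit 3, under G) Study Procedures, gives the sequence. Discs are separated from the mouth guard and labelled: "The back side of each disc will be numbered 1-64 and the subject and intraoral location will be recorded". They are randomised in R so that each subject gives two discs to each of the four groups, then treated, rinsed and stained. For imaging, "The discs will be observed in a fluorescence microscope equipped with FITC/TRITC filter sets". For measurement, "Percent biofilm covered area will be calculated with digital image analysis software (ImageJ, NIH"). The section gives the dye components, incubation time, filter sets and microscope model. It does not say who treats, images or measures the discs, or what that person knows about allocation.

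The Access item limits data to study staff without distinguishing roles. In the available text, the only use of the word blinded is in the title of a cited reference.

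**The concern.** The stated hypothesis is directional: the laser should clear more biofilm than the carbon fiber curette. Turning a fluorescence image into a percent area takes decisions, at least on where the threshold lies. If the person deciding knows the treatment, a small and quite unconscious tendency can enter disc by disc.

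Such a tendency adds directly to the Er:YAG-curette difference. Randomising discs within subject balances subject and mouth position before treatment; it cannot undo a difference introduced at reading. Neither repeated-measures ANOVA nor Friedman's test can tell it from a treatment effect. Because the primary outcome rests wholly on this reading, masking of the reader belongs in the protocol.

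**Working it through.** **1. Reading the steps for masking.**

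- Labelling: numbers 1-64 are tied to subject and location. They carry no treatment information in themselves, so they could act as a code. No sentence says the number-to-treatment list is kept from the reader.
- Treatment: whoever treats a disc must know its group. If that person also reads it, the number hides nothing.
- Imaging and measurement: operator and masking are not stated.
- ImageJ: no threshold rule is given, so the software alone does not remove the reader's discretion.

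**2. The plan's own figures.** B) Power Calculation gives "a sample of 8 subjects, allowing for ~20% dropout with a final projected sample size of 6", with 8 discs each. The counts reproduce: 8 × 8 = 64 discs, 64/4 = 16 per group, and 6/(1 − 0.20) = 7.5, rounded up to 8. The power over 99% can be neither reproduced nor refuted, because its means and SDs come from a cited study and are not shown.

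**3. What an assumed bias could do (illustration only).** The documents give no bias size. Let d be the bias toward the laser in SDs of the subject-level paired difference (mean of two discs per group), with d = 0.5 and 1 assumed. C) Statistical analysis names no pairwise test, so take a paired t-test at two-sided 0.05. With no true difference:

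P(false laser win) = P(T > t₀.₉₇₅) with n − 1 df and noncentrality d√n.

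- n = 6: critical value 2.571; noncentrality 1.22 or 2.45; probability 16.9% or 50.7% (2.5% without bias).
- n = 8: critical value 2.365; noncentrality 1.41 or 2.83; probability 23.1% or 68.1% (2.5% without bias).

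Other tests give other values. Using the pooled repeated-measures error: 20.8% or 63.0% (n = 6), 27.1% or 77.0% (n = 8). With a two-group Friedman test, normal differences and n = 6, all six subjects must agree: Φ(0.5)⁶ = 0.691⁶ = 10.9%, or 0.841⁶ = 35.5%. With n = 8 the large-sample p-value rejects at 7 of 8 (p = 0.034), giving 23.9% or 63.0%. The exact p-value at 7 of 8 is 0.070, so only 8 of 8 rejects, giving 0.691⁸ ≈ 5% or 0.841⁸ ≈ 25%.

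**4. What the same bias does if the true difference is large.** If the stated power over 99% applied to this contrast, the paired t-test would need a true difference of at least 2.24 SD (n = 6) or 1.79 SD (n = 8). A bias toward the laser then inflates the estimate by at most:

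- n = 6: 0.5/2.24 = 22%, or 1/2.24 = 45%.
- n = 8: 0.5/1.79 = 28%, or 1/1.79 = 56%.

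Across the three tests (Friedman with large-sample p-values) the required difference is 1.6 to 2.9 SD, and the ceiling on inflation is 17% to 31% for 0.5 SD and 34% to 63% for 1 SD. In that setting the test already finds for the laser in over 99% of trials, so a bias toward it has almost no room to change the conclusion.

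**The case against.** **The silence may not be the plan's.** The text between Informed Consent and the paragraph on subject identification numbers was not available, and what follows it concerns identification numbers and group assignment. A masking statement there cannot be excluded. A reader might infer that the study is unmasked by design; the documents do not support that, only that the available text does not state masking. The laboratory section shows no gap and is the natural home for such a statement, so the missing text lowers certainty without closing the point.

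**The false-win rates prove little.** A reader might infer from 51% or 77% that the result is likely to be wrong. Those figures assume no true difference, an invented bias and pairwise tests the plan does not name, and one of them falls steeply under exact p-values. They show what is possible, not what is likely. This objection stands in full.

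**The other image settings are mostly laboratory detail.** A reader might infer that the outcome itself is undefined. That goes too far. The outcome is a percentage of the disc, whose size is given ("Titanium discs (5mm diameter, 1 mm thick"), which points to the whole disc. The dye kits "provide a novel two-color fluorescence assay of bacterial viability", but the outcome is coverage rather than viability and both filter sets are used, so counting both signals is the natural reading. An automatic whole-disc threshold is possible. The threshold rule is still not stated, and it matters here because an unmasked reader could choose it disc by disc.

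**Masking cannot be complete.** This is true. Instrument marks, or heavy biofilm on untreated control discs, may reveal the group, and re-labelling files does not mask image capture. Partial masking with fixed settings still removes much of the discretion.

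**Conclusion.** The point holds as a cheap improvement. The available text does not state that the imager or reader of the primary outcome is unaware of treatment, does not say that the number-to-treatment link is withheld, and fixes no threshold rule. An unmasked reader could therefore shift the Er:YAG-curette difference.

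The size of any shift is unknown, and nothing in the documents shows that one would occur. If the true difference is as large as the stated power implies, bias would more likely inflate the estimate than change the conclusion. That reassurance rests on the power statement applying to the laser-curette contrast, which cannot be checked from the documents. Certainty is moderate because part of the text was not available.

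**What to change.** Add a short paragraph to the laboratory section after Visit 3:

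1. Save images under a code that carries no treatment information. Numbers 1-64 can serve for this.
2. Have a script re-label the image files in random order before measurement.
3. Withhold the re-labelling key from the reader until all percent-area values are locked. Where the reader did not treat the discs, withhold the number-to-treatment list as well. The person treating the discs keeps the allocation.
4. Apply one pre-set imaging and threshold rule to all discs, because re-labelling does not mask image capture.

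The cost is one paragraph and a simple script, with no extra reader, subject or disc and no change to the sample size. The downside is that masking stays partial, and the text should say so. If the text not available here already contains a masking statement, a cross-reference and the threshold rule would be enough.
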